4.1 OVERALL DESIGN

In aim 1, with relevant stakeholders in adolescent HIV, we will collaboratively develop the DiSC intervention, then adapt and pilot test the intervention.

In aim 2, we will conduct a cluster randomized trial (cRCT) in up to 24 sites in western Kenya (12 randomized to intervention and 12 to control) (Figure 1).

Figure 1: Study design, main activities, and outcomes

Adapted from NIH Behavioral and Social Intervention Clinical Trial Protocol Template v3.0 - 20180827

Study hypothesis

- Primary and secondary outcomes: We hypothesize that the DiSC intervention will result in better retention, adherence and viral suppression among adolescents in the intervention sites compare to those in control sites. Hypothesized psychosocial outcomes will include better psychosocial and family support, mental health, family support and adolescent self-efficacy.
- We hypothesize the DiSC intervention will be associated with improved clinic efficiency (client wait time), and will be cost effective.
- The DiSC Intervention will be feasible, acceptable to HCW and adolescents but will require clinic specific intervention adaptations.

Randomization

Up to 24 clinics will be randomized in a 1:1 ratio using computer generated random numbers to either intervention or control, using restricted randomization to balance by county, aiming to balance the numbers of clinics from each county between arms. Timing of randomization will be prior to study start. Randomization will be done at the University of Washington by a biostatistician not involved in study procedures. A list of clinics with their allocation arms will be sent to the study team. We will perform individual substitutions of sites on a case by case basis, as needed (e.g. if the site no longer meets an eligibility criterion). The intervention is administered at the clinic-level; it is not possible to blind participating clinics or study team members.

Study intervention

The DiSC intervention is comprised of a system to assign adolescents to care based on their health needs and the different levels of care for each assignment group. Control sites will continue with standard of care approaches for adolescent clinic visits (usually 1-3 monthly visits) regardless of health care needs and additional support as needed.

Analysis

Adapted from NIH Behavioral and Social Intervention Clinical Trial Protocol Template v3.0 - 20180827

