9.2 SAMPLE SIZE DETERMINATION

Sample Size and Power for primary outcome

In our sample of HIV care facilities with >1,000 clients enrolled overall, we anticipate at least 10% will be eligible adolescents and young adults or about 100-200 AYA per clinic on average. Based on our UG3 data, we assume that 75% will be in care (not LTFU) and viral suppression of 64% (85% suppressed x 75% actively in care). Given a minimum of 20 facilities in the trial (minimum 10 per arm), we estimated the minimum average number of AYA per facility to detect a 15-20% change in retention using EMR data. We assumed 80% power, an $\alpha=0.05$ and coefficient of

Adapted from NIH Behavioral and Social Intervention Clinical Trial Protocol Template v3.0 - 20180827

variation of 0.15. In table 3a below, we can detect a 17% percentage point different (75% to 93%) with an average of 100 AYA per facility and 20 facilities. The same estimates hold for as few as 50 AYA per arm and up to 170 per arm. Detecting less than a 17% percentage point difference would require more facilities per arm or at least 180 AYA per facility.

Secondary outcomes and assumptions:

Viral suppression: An average of 50 AYA VL records per facility and a minimum of 10 facilities per arm would be sufficient to detect a change from 64% to 81%, assuming 80% power, an $\alpha=0.05$ and coefficient of variation of 0.15.

Cohort analyses: Based on UG3 enrollment data in the AYA cohort, we assume that about 50% of the total AYA clinic population to enroll in the cohort and set 50 as the average enrollment target per facility. Separate power and sample size calculations will be performed based on the specific exposure and outcome. When the intervention is the exposure, we will assume to have adequate power to detect at least a 17% percentage point difference in proximate outcomes (e.g. implementation and client outcomes)

Table 3a: Minimum Sample of AYA per Facility for the Primary ITT Analysis of Retention

	Retention % in the intervention arm	n=100 AYA per facility	Facilities per arm	n=50 AYA per facility	Facilities per arm
75%	90%	100	13	50	14
75%	92%	100	11	50	12
75%	93%	100	10	50	10

Table 3b: Summary of sample size estimates by outcome

Outcome	Source	Sample size	
		Intervention	Control
Retention	EMR data	3000	3000
Unsuppressed VL	EMR data	3000	3000
Mediators and secondary outcomes	Adolescent surveys	1500	1500
	Caregiver surveys	450	450
Implementation outcomes	HCW surveys	120	120
	HCW implementation logs	12	0

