9.4.2 ANALYSIS OF THE PRIMARY ENDPOINT(S)

Adapted from NIH Behavioral and Social Intervention Clinical Trial Protocol Template v3.0 - 20180827

Mixed effects regression models will be used to compare the number of missed visits between arms, accounting for clustering by individual and clinic. LTFU will be compared using cox proportional hazards regression. Death or transfers will be censored. Sub-group analyses will be performed by gender and age-group. Facility factors, including concurrent adolescent-friendly services and high/low performance will be evaluated as moderators of intervention effectiveness.

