9.4.7 SUB-GROUP ANALYSES

Adapted from NIH Behavioral and Social Intervention Clinical Trial Protocol Template v3.0 - 20180827

Subgroup analysis will be performed by gender and age group for primary and secondary outcomes. As with the primary analysis, sub-group analysis will be adjusted to account for clustering.

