3.4. Analysis of retention

Retention will be evaluated using an indicator of missed visits. A missed visit will be defined as a participant not seen within 30 days of a scheduled visit during follow-up since the first stepped care visit to 12 months. Each scheduled visit will be classified as missed versus not missed and analysis will use repeated measures per participant. The proportion of missed visits will be compared between study arms using mixed-effects Poisson regression with random effects for facility and participant and robust standard errors.

Sub-group analyses for retention will be performed by gender and age-group. Facility factors, including concurrent adolescent-friendly services and high/low performance will be evaluated as modifiers of intervention effectiveness.

Table 4. Analysis of missed visits

	Overall	Control	Intervention	Intervention vs. control
Missed visits per participant				^a RR (95% CI)
Median (IQR)				
Number of scheduled visits				
Number of missed visits (%)				
Missed visits over all participants				
Count (proportion)				
Number of scheduled visits				
Number of missed visits (%)				
Number of AYA ever missed a visit (%)				

^a Estimated by mixed-effects Poisson regression with random effects for facility and participant and robust standard errors

*Excluding TCA that had miss/no-miss status censored or missing

*Models adjusted for any factors differing between arm with statistical significance at enrollment

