3.5. Analysis of secondary study outcomes

3.5.1. Loss to follow-up:

- Loss to follow-up will be defined as a participant missed a visit and did not return to care within the 12-month study period. The proportion of loss to follow-up during 12-month study interval (window up to 12 months +30 days) will be compared between study arms using Poisson regression with robust errors.
- Time to loss to follow-up will be compared between arms by survival curves, and death or transfers will be censored. The hazard of loss to follow-up will be compared between study arms using Cox proportional hazards regression.

3.5.2. Viral non-suppression:

- Viral non-suppression will be defined as having HIV viral loads (VL) >1,000 copies/mL. Each VL testing result will be classified as VL suppressed vs. unsuppressed. The proportion of viral non-suppression during follow-up will be compared between study arms using mixed-effects Poisson regression with random effects for facility and participant and robust standard errors.

3.5.3. Receiving differentiated care:

- Receiving differentiated care will be defined in two ways. One approach will evaluate the next visit appointment date (scheduled inter-visit interval) – visits scheduled for ≥ 3 months after visit will be considered as differentiated care, in comparison to monthly visits recommended for AYA in current guidelines. The second approach will use the variable ‘fast-track’ at each visit – ‘fast track’ visits are considered as a component of differentiated care. Two analyses will be conducted (one for long scheduled inter-visit interval and one for ‘fast track’), each will be compared between study arms using mixed-effects Poisson regression with random effects for facility and participant and robust standard errors.

3.5.4. Adherence:

- Adherence will be evaluated using the proportion of days of pill dosing over days of inter-visit interval. The level of adherence during the past inter-visit interval will be assessed at each visit. A proportion over 80% as good adherence. The dichotomized adherence will be compared between arms using mixed-effects Poisson regression with random effects for facility and participant and robust standard errors.

Table 5. Analysis of secondary study outcomes

Loss to follow-up				
	Overall	Control	Intervention	Intervention vs. control
	Count (proportion)			^a RR (95% CI) ^b HR (95% CI)
Event Person-year Cumulative incidence Incidence rate (per 100 person-years)				
Viral non-suppression				

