	Overall	Control	Intervention	Intervention vs. control
	Count (proportion) / Median (IQR)			^c RR (95% CI)
Per participant Number of viral load assays				
Over all participants Number of viral load assays Number of non-suppression results (%)				
Differentiated care: long-interval visits scheduled				
	Overall	Control	Intervention	Intervention vs. control
	Count (proportion) / Median (IQR)			^c RR (95% CI)
Per participant Number of scheduled visits				
Over all participants Number of scheduled visits Number of long-duration interval (%)				
Differentiated care: fast-track visits				
	Overall	Control	Intervention	Intervention vs. control

DiSC UH3 Statistical Analysis Plan (SAP)

	Count (proportion) / Median (IQR)			°RR (95% CI)
Per participant Number of visits with non-missing care model				
Over all participants Number of visits with non-missing care model Number of fast-track visits (%)				
Adherence				
	Overall	Control	Intervention	Intervention vs. control
	Count (proportion) / Median (IQR)			°RR (95% CI)
Per participant Number of intervals with good adherence				
Over all participants Number of intervals with good adherence Number of intervals with good adherence (%)				

^a Estimated by Poisson regression with robust errors

^b Estimated by Cox proportional hazards regression

^c Estimated by mixed-effects Poisson regression models with random effects for facility and participant and robust standard errors

*Models adjusted for any factors differing between arm with statistical significance at enrollment

Section 4. Missing data

While we will attempt to follow all participants at 12 months, we anticipate that EMR data and VL data may be incomplete for some participants might be a challenge due to participant loss to follow-up – either due to loss from care, or silent transfer to another facility. Due to the level of missingness we expect, we will not conduct any formal imputation.

Section 5. Safety monitoring

Adverse and severe adverse events, including social harms such as violence or breach of confidentiality, will be monitored as they arise, and unblinded results will be reviewed by the DSMB. The DSMB will make recommendations regarding any imbalances in safety outcomes.

SAE #	PTIDNO	Study arm	SAE description	Onset date	Duration (days / unresolved)	Onset since randomization (days)	Relatedness to study

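### SAP 3.5.1 specifies no clinic-level clustering for either loss-to-follow-up analysis in a clinic-randomised trial; run that way, type I error is about 21% to 72% at the plan's own planning values

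*SAP*

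**What the plan says.** The clinic is the unit of randomisation (Protocol 4.1): "Up to 24 clinics will be randomized in a 1:1 ratio".

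SAP 3.5.1 plans two comparisons of LTFU:

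- The 12-month proportion "will be compared between study arms using Poisson regression with robust errors". No clustering unit is named.
- For time to LTFU: "The hazard of loss to follow-up will be compared between study arms using Cox proportional hazards regression". There is no frailty, facility term or robust variance.

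The Table 5 footnotes repeat this. Footnote a gives Poisson with robust errors, and footnote b reads "Estimated by Cox proportional hazards regression". Footnote c, the mixed model, is kept for the other outcomes.

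Elsewhere the SAP does handle clustering. Missed visits, the primary outcome in SAP 3.4, are analysed by "mixed-effects Poisson regression with random effects for facility and participant and robust standard errors". SAP 3.5.2 to 3.5.4 use the same model for viral non-suppression, both differentiated-care measures and adherence.

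Protocol 9.4.2 shows the same split. It attaches clustering by individual and clinic to the missed-visits model, then says "LTFU will be compared using cox proportional hazards regression" without mentioning clinics. Protocol 9.4.7 adds: "As with the primary analysis, sub-group analysis will be adjusted to account for clustering".

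**The concern.** Participants in one clinic share staff, services and catchment, so their outcomes are correlated. A model that treats them as independent understates the standard error of the arm comparison, and chance differences between clinics can then be reported as intervention effects. LTFU is the only outcome in the SAP left without a facility term.

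The SAP ranks LTFU as secondary (2.1, Table 1). It is still close to the centre of the trial. Protocol 9.4.2 lists the Cox comparison under the primary endpoint heading, and the sample size in SAP 2.2.1 assumes that 75% are still in care, that is not LTFU, at 12 months. The plan allows for between-clinic variation when it sizes the trial on this proportion, but not when it tests it.

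**Working it through.** **Inputs.** 25% LTFU, as the complement of 75% in care (SAP 2.2.1). Between-clinic variation of 0.10 and 0.15, and m = 50, 100, 150 or 200 participants per clinic (sample-size table, SAP 2.2.2); SAP 2.2.1 expects about 100 to 200. Alpha is 0.05, taken as two-sided because the SAP does not say. Clinics: 24, with 20 as the Protocol 9.2 minimum.

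**Step 1: what 0.10 and 0.15 mean.** SAP 2.2.1 calls them coefficients of variation (CV); the table labels them ICC. Read as an ICC,

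facilities per arm = 7.849 × [p0(1−p0) + p1(1−p1)] / (p0−p1)² × [1 + (m−1)·ICC] / m, rounded up.

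- 75% vs 90%, m = 50, 0.10: 7.849 × 0.2775 / 0.0225 = 96.80; × 5.9 / 50 = 11.42, so 12. Printed: 12.
- 75% vs 92%, m = 50, 0.15: 7.849 × 0.2611 / 0.0289 = 70.91; × 8.35 / 50 = 11.84, so 12. Printed: 12.

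This matches 70 of the 72 cells in the 75% block, the other two within 1. The CV formula, including its usual added 1, matches 5 of 72. Protocol Table 3a, by contrast, fits CV 0.15 with that added 1 in 5 of 6 cells; the sixth computes to 10.004, which rounds up to 11, against a printed 10. Both readings are therefore carried forward.

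**Step 2: CV to ICC.** ICC = (CV × p)² / [p(1−p)].

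- CV 0.10 on 75%: 0.075² / 0.1875 = 0.03.
- CV 0.15 on 75%: 0.1125² / 0.1875 = 0.0675.
- Same CVs on 25% LTFU: 0.025² / 0.1875 = 0.0033; 0.0375² / 0.1875 = 0.0075.

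**Step 3: type I error when clinics are ignored.** Design effect DE = 1 + (m−1)·ICC. The standard error is too small by √DE, and type I error = 2[1 − Φ(1.96/√DE)]. For example, ICC 0.03 and m = 50 give DE = 2.47, √DE = 1.57 and 21.2%. ICC 0.15 and m = 200 give DE = 30.85, √DE = 5.55 and 72.4%.

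| Reading | ICC | m=50 | m=100 | m=150 | m=200 | SE too small by |
|---|---|---|---|---|---|---|
| CV 0.10 on 75% | 0.03 | 21.2% | 32.5% | 40.2% | 45.8% | 1.57–2.64 |
| CV 0.15 on 75% | 0.0675 | 34.5% | 48.0% | 55.6% | 60.6% | 2.08–3.80 |
| ICC 0.10 | 0.10 | 42.0% | 55.3% | 62.3% | 66.8% | 2.43–4.57 |
| ICC 0.15 | 0.15 | 49.8% | 62.3% | 68.5% | 72.4% | 2.89–5.55 |
| CV 0.10 on 25% | 0.0033 | 6.9% | 8.9% | 10.9% | 12.9% | 1.08–1.29 |
| CV 0.15 on 25% | 0.0075 | 9.4% | 13.8% | 17.8% | 21.4% | 1.17–1.58 |

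**Step 4: simulation.** Null trials with 24 equal-sized clinics and beta-distributed clinic risk around 25% were run twice. One set had 1,500 trials per setting, with 5% censored for death or transfer in the Cox model (an assumption, not in the documents). The other had 4,000 per setting, using the Cox score test. Rejection rates, first / second set:

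| Setting | Unclustered Poisson | Plain Cox |
|---|---|---|
| ICC 0.03, m=50 | 20.6% / 21.5% | 19.7% / 22.0% |
| ICC 0.0675, m=200 | 61.3% / 60.9% | 60.8% / 61.0% |
| ICC 0.10, m=200 | 66.8% / 66.1% | 67.1% / 66.2% |
| ICC 0.15, m=200 | 73.5% / 72.7% | 73.0% / 72.9% |
| ICC 0.0033, m=50 | 6.8% / 5.7% | 7.5% / 5.7% |

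**Step 5: after correction.** Clinic-clustered variance multiplied by J/(J−2) and referred to t with J−2 degrees of freedom (J = number of clinics, 20 and 24) gave 4.3% to 6.4% for the Poisson model and 4.0% to 6.3% for Cox. A t-test on clinic proportions with 22 degrees of freedom gave 4.1% to 5.3%.

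**The case against.** **The risk ratio is ambiguous rather than wrong.** Robust errors can be clustered on facility, and that would largely repair it. This stands as a reading. But with one row per participant the default robust error ignores clinics, and the SAP names no unit. The Cox model has no such wording to interpret.

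**The intent to cluster is visible.** Protocol section 9 only summarises the SAP. Protocol 9.4.3 is silent on clustering for other secondary outcomes, and the SAP then supplies facility random effects for viral non-suppression and adherence. Protocol 9.4.7 points the same way. All fair, but 9.4.7 covers sub-group analyses, and no SAP section carries a general rule that reaches 3.5.1.

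**The headline range joins two readings.** It does: 21% to 61% under CV and 42% to 72% under ICC. The 72% also needs the highest ICC and the largest tabled clinic. These are planning values, not estimates of variation in LTFU. Applying the CV to the 25% lost gives 7% to 21%. However, the plan states its CV for retention, and complementary proportions have the same ICC.

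**Restriction by county and baseline adjustment could reduce the inflation.** Neither was simulated, and the documents give no county share. As an illustration, suppose county removed half the between-clinic variance, so DE = (1 − ICC) + m·ICC/2. At ICC 0.03 and m = 50, DE = 0.97 + 0.75 = 1.72, about 13.5%. At ICC 0.15 and m = 200, DE = 0.85 + 15 = 15.85, about 62%. The inflation shrinks but remains.

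**The primary analysis is sound.** Correct: missed visits have a facility random effect.

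**Conclusion.** The concern holds. The Cox LTFU analysis is wrong as written for a clinic-randomised trial, and the Poisson LTFU analysis is under-specified in a way that its default implementation would make wrong. If clinics are ignored, type I error is about 21% to 72% across the plan's planning values and 50 to 200 participants per clinic. At the expected 100 to 200 per clinic, the lowest value is about 33%.

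These figures assume a two-sided 5% test, equal clinic sizes, the planning values applied to retention, and no gain from county restriction or covariate adjustment. The confidence intervals and p-values for one secondary outcome are at stake, not the primary missed-visits result. The correction should be made before the LTFU analysis is run.

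**What to change.** In SAP 3.5.1 and Table 5 footnotes a and b:

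- **Risk ratio:** use a facility random effect, or state that the robust variance is clustered on facility.
- **Hazard ratio:** use a facility shared frailty, or facility-clustered variance.
- **If clustered variance is used:** add a small-sample correction with degrees of freedom equal to randomised clinics minus 2 (24 − 2 = 22, or 20 − 2 = 18 at the Protocol minimum).

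Name one option for each model in advance. A frailty hazard ratio is conditional on clinic and a clustered-variance hazard ratio is marginal, so they are not interchangeable. Only the clustered-variance option was checked here for type I error; the random-effect and frailty options were not simulated. Other accepted small-sample corrections would also serve.

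A matching clause in Protocol 9.4.2 would keep the documents aligned, although the SAP is where the method is set.

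The cost is one or two sentences, two footnotes and a clause. No new data are needed. The downside is wider confidence intervals for LTFU.

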6 STUDY INTERVENTION(S) OR EXPERIMENTAL MANIPULATION(S)

6.1 STUDY INTERVENTION(S) OR EXPERIMENTAL MANIPULATION(S) ADMINISTRATION

6.1.1 STUDY INTERVENTION OR EXPERIMENTAL MANIPULATION DESCRIPTION

The Data-informed Stepped Care (DiSC) intervention is comprised of a system to assign ALHIV to different levels of care, or “steps”, depending on their current and anticipated health care needs. Stepped care is a model grounded in Stages of Change Theory and has been used in mental health fields to organize provision of services, and to support clients, HCWs, and caregivers to identify interventions tailored to individual need. HCWs at participating sites will assign ALHIV to different levels or intensity of HIV services. The trajectory of services moves from a relative position of ALHIV autonomy to more intensive service provision. Intervention steps could start with multi-month refills or community treatment delivery, then social support activities (support groups, life skills activities), progress to individualized services (text messaging, ‘big brother/sister’ older peer support, motivational interviewing), and ultimately a case management approach involving referrals to specialized care like mental health or gender-based violence services, individualized counseling, and active tracking of individual participation in support and care services. The stepped care framework is designed to be flexible, to accommodate variable

Adapted from NIH Behavioral and Social Intervention Clinical Trial Protocol Template v3.0 - 20180827

individual and social support services available at each facility. A sample of potential intervention steps is presented below:

Sample intervention steps

Levels	Criteria for eligibility	Regular care	Additional HCW provided	Additional clinic recommended
Stepped down care	Meets MoH criteria except age	-Differentiated care	None	-Support groups (optional)
Not retained	At risk for loss	-3 monthly visits	-Pre-clinic reminders (text) -Individual peer support -3 monthly adherence counseling	-Support group
Viral failure	At risk for viral failure OR VL under 1000 but detectable	-Monthly visits (6 weekly for school going)	-Monthly adherence counseling -Motivational interviewing (one round of several sessions) OR Coaching -Individualized ART pick-up strategies	-Support group -Caregiver or support person DOTS

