Failed	Unsuppressed at last measure	-Monthly visits (6 weekly for school going)	-2 weekly adherence sessions (could make some on phone) -Accelerated repeat test timeline (3 month) -Prompt switch after second test -Case manager -DOTS by HCW (or caregiver/family)	-Support group -Special treatment failure support groups -Home visit by HCW -Viremia clinics

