Program records: We will abstract ALHIV medical record data at baseline and regular intervals throughout the study. Data from all adolescents with at least 1 clinic record within the 12-month period prior to the first data abstraction date will be included. Data will be abstracted at the facility or at the office of the technical partner that supports the EMR system at the facility. The EMR system captures data on client anthropometric measures, demographics, HIV testing history, family members, clinical history, ART adherence data, laboratory data, CD4 count, transfers, and discontinuations. Routine viral load testing (done 6 months after ART initiation, then annually) will be abstracted from the EMR, if available, or NASCOP's laboratory database. If EMR data is unavailable, paper medical records will be abstracted using mobile REDCap which enables automatic upload of data to a secure, password-protected study server.

Adolescent behavioral surveys: Adolescent surveys will include questions on socio-demographics, health care use, stigma, sexual behavior, psychosocial support, mental health, personal health knowledge, HIV disclosure and medication adherence. Surveys will be administered every 6 months either in-person or over phone by a trained study staff. Survey visits will coincide with clinic visits as much as possible.

Caregiver behavioral surveys: Caregiver surveys will include questions on socio-demographics and family, caregiver roles, HIV disclosure, HIV care experience, disclosure, social support, mental health, HIV testing and awareness, personal health and HIV experience, HIV stigma, ART knowledge and adherence. Surveys will be administered every 12 months either in-person or over phone by a trained study staff. Survey visits will coincide with clinic visits as much as possible.

Data on health services and implementation outcomes will be collected as previously described (see section 6.2).

To track implementation, the following surveys will be conducted:

Facility surveys: Facility managers will complete baseline and annual facility surveys to understand baseline resource capacity to implement future interventions and modifiable and non-modifiable health system factors. Variables will include availability of youth-friendly services, management and referral systems, and differentiated care services available.

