2.1. Summary of primary and secondary outcomes

Table 1. Outcome definitions and assessment

Outcome	Indicator	Source	Timing
Primary outcome			
Retention in care	Missed visits: Not seen within 30 days of a scheduled visit.	EMR data (Visit Date, TCA)	All visits occurring during the 12-month period after the study enrollment visit*
Secondary outcomes			
Loss to follow-up	Not return to care within the 12 months study interval	EMR data (Visit Date, TCA)	All visits after the first study visit until event or end of follow-up at 12 months. Participants marked as 'transferred out' or 'died' will be censored.
Viral non-suppression	Having HIV viral load (VL) >1,000 copies/mL	NASCOP data, abstraction of paper records	All visits from enrollment to 12 months follow-up*
Receiving differentiated care	
 Long inter-visit interval Fast-track visit 	EMR data (TCA, Care Model)	All visits from enrollment to 12 months follow-up*
Adherence	Pill coverage estimated by days of dosing and inter-visit interval since last visit >80%	EMR data (Visit Date, next Visit Date, Duration)	All visits from enrollment to 12 months follow-up*

*time window up to 12 months + 30 days

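### Counting every viral load result lets outcome-triggered repeat testing in DiSC clinics bias the non-suppression ratio toward harm, if control clinics repeat later or less often

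*SAP*

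**What the plan says.** SAP section 3.5.2 defines non-suppression as a VL above 1,000 copies/mL and scores results, not people: "Each VL testing result will be classified as VL suppressed vs. unsuppressed". SAP Table 1 in section 2.1 sets the timing as "All visits from enrollment to 12 months follow-up", with a "time window up to 12 months + 30 days". The arms are compared by mixed-effects Poisson regression with random effects for facility and participant and robust standard errors. Table 5 reports unsuppressed results as a percentage of assays. No rule selects one result per person, sets repeat tests aside or weights by number of tests, and there is no sensitivity analysis.

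Three protocol statements decide how many results a person contributes:

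- Section 8.1: "Routine viral load testing (done 6 months after ART initiation, then annually"). An adolescent established on ART therefore has about one routine result in the window.
- Section 6.1.1, highest step: the trigger is "Unsuppressed at last measure", and the added services include "Accelerated repeat test timeline (3 month"). The table is introduced with the words "A sample of potential intervention steps is presented below".
- Section 4.1: "Control sites will continue with standard of care approaches for adolescent clinic visits". Neither document says how soon a control clinic repeats a VL after an unsuppressed result.

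The protocol synopsis and section 9.4.3 state the endpoint as the proportion of adolescents suppressed at 6 and 12 months, which is a participant-level quantity.

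**The concern.** Under the sample steps, the number of results a person contributes depends on arm and on the outcome itself. A suppressed adolescent in either arm contributes about one result. An unsuppressed adolescent in a DiSC clinic can contribute a second, and that second result is more likely than average to be unsuppressed. The randomised intervention would then add unsuppressed results to its own arm.

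Robust standard errors do not correct a biased point estimate. A participant random effect can help only where there are several results per person to inform it, and most participants have one. The possible consequences are an apparent excess of non-suppression when there is none, or a real benefit masked.

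**Working it through.** **The plan's own figure.** SAP section 2.2.2 gives 11 facilities per arm to detect 64% versus 82% suppression with 50 VL records per facility at 0.10. Unpooled two-proportion formula: 7.849 × (0.64×0.36 + 0.82×0.18) / 0.18² = 7.849 × 0.378 / 0.0324 = 91.6 per arm. Times the design effect 1 + 49×0.10 = 5.9, this is 540.3; divided by 50 it is 10.81, rounded up to 11. The figure reproduces. The calculation has no second level for repeated results within a person and no difference between arms in results per person, so it describes one result per participant.

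**Inputs for the bias.**

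- p = 0.15, non-suppression at the first test (protocol section 9.2 assumes 85% suppressed among those in care).
- Window of 13 months (SAP Table 1).
- First test uniform over months 0 to 12 (assumption).
- q, the chance that a repeat is again unsuppressed: 0.3 to 0.9 (assumption; not in the documents).
- r, the share of repeats that fall inside the window. A 3-month repeat fits if the first test is by month 10, so r = 10/12 = 0.833.

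**Formula, no true effect, one repeat in DiSC and none in control.** Results per person in DiSC are 1 + rp = 1.125, against 1.00. Unsuppressed results per person are p(1 + rq). The assay-level ratio is therefore (1 + rq)/(1 + rp), which exceeds 1 whenever q > p. For q = 0.5 it is 1.417/1.125 = 1.26. The last column is a simulation of 400,000 people per arm, fitted by Poisson regression with a participant random intercept.

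| q | DiSC unsuppressed results (control 15%) | Ratio by formula | Mixed-model ratio |
|---|---|---|---|
| 0.3 | 16.7% | 1.11 | 1.12 |
| 0.5 | 18.9% | 1.26 | 1.27 |
| 0.7 | 21.1% | 1.41 | 1.35 |
| 0.9 | 23.3% | 1.56 | 1.49 |

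The random effect removes nothing at low q and only part at high q. If DiSC repeats continue while the result stays unsuppressed, the mixed-model ratios are 1.16, 1.31, 1.49 and 1.66.

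**If controls repeat too.** A 6-month repeat fits if the first test is by month 7, a share of 7/12 = 0.583. With one repeat per arm and q = 0.5, the control factor is 1.292/1.0875 = 1.188, and the ratio is 1.259/1.188 = 1.06. The same sum gives 1.03 at q = 0.3 and 1.11 at q = 0.9. With continuing repeats in both arms, the simulated mixed-model ratio is 1.06 to 1.22. With a 3-month repeat in both arms it is 1.00.

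**Alternatives to counting every result.**

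- *Last result per person.* With one DiSC repeat and no control repeat, the ratio is 1 − r + rq: 0.42 at q = 0.3 and 0.92 at q = 0.9. Simulated values, including continuing repeats, run from 0.29 to 0.91. The bias reverses, because only DiSC adolescents get a second chance to re-suppress in the window.
- *First result per person.* The ratio is 0.99 to 1.01 if first-test timing is unrelated to earlier results. However, an unsuppressed VL before enrollment can also trigger an early test in DiSC. In a simulation that adds a pre-enrollment VL, the first-result ratio is 1.09 to 1.17 with no early control repeat and 1.03 to 1.05 with 6-month control repeats.
- *First result at 6 months or later.* In the same simulation the ratio is 0.66 to 0.99, because DiSC adolescents with prior failure who were tested early drop out.
- *First result among those suppressed at the last pre-enrollment VL.* The ratio is 1.00 to 1.01, because nothing in their testing schedule differs by arm.

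**The case against.** The strongest reply is that the premise is not settled. The step table is a sample, and section 6.2.1 leaves the number of steps and the assignment system to a workshop and pilot. Calling the repeat accelerated implies that standard care repeats more slowly, not that it never repeats. Section 8.1 names routine testing as what will be abstracted, so off-schedule repeats might not enter the data at all. All of this stands, and it makes the size conditional. It does not remove the point: these are the only steps described, the SAP takes all visits and every result, and nothing in it separates routine from repeat tests.

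A second reply is that Table 5 already shows assays per participant by arm. In the one-repeat case only 0.15 × 0.833 = 12.5% of DiSC adolescents have a second result. The median and both quartiles would be 1 in each arm, so the imbalance would hardly show there, and displaying it would not correct the ratio.

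A reader might infer more than the documents support:

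- *That unsuppressed DiSC adolescents all count several times.* Under the set-up above, 2/12 = 17% of them are first tested after month 10 and count once.
- *That repeats continue indefinitely.* The same table cell provides for a treatment switch after a second test, which suggests one repeat, so the lower set of ratios is the better guide.
- *That this is the leading clinical secondary outcome.* SAP Table 1 sets no hierarchy.

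**Conclusion.** The point holds in conditional form. If the final DiSC steps keep an accelerated repeat for unsuppressed adolescents, control clinics repeat later or less often, and those repeats enter the dataset, the assay-level ratio in SAP section 3.5.2 is biased toward harm. With no true effect and 15% non-suppression, the mixed-model ratio is about 1.1 to 1.5 with one repeat and no control repeat, 1.06 to 1.22 with 6-month control repeats, and 1.0 with equal schedules. At a ratio of 1.27, a true reduction of about one fifth (1 − 1/1.27 = 21%) would look like no effect.

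The documents do not support saying that the trial will show false harm. They do not give q, the control repeat timing or the distribution of first-test times. The primary outcome, retention, is not affected. This should be fixed, as a matter for a secondary outcome, with medium confidence.

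**What to change.** In SAP section 3.5.2 and Table 5:

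1. Make the participant the unit. Analyse one pre-specified result each, the first VL drawn after the enrollment visit, in Poisson regression with a facility random effect and robust standard errors.
2. Stratify by or adjust for the last pre-enrollment VL status (suppressed, unsuppressed, none on record). Also report the comparison among those suppressed at that test, where test timing should not depend on arm.
3. Report repeats after an unsuppressed result descriptively by arm: number of repeats and share re-suppressed. Show the distribution of assays per participant, not only the median and IQR.
4. Keep the all-results model as a sensitivity analysis only. Use neither the last result nor a restriction to first results at 6 months or later.
5. State the final DiSC repeat-testing rule, the control clinics' practice, and whether off-schedule tests are abstracted, so that readers can judge the remaining imbalance.

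The cost is SAP wording and one re-specified model on records that the protocol already plans to abstract. The comparison uses fewer records. Some first results will fall before DiSC could act, which dilutes a real effect. The analysis of those previously suppressed leaves out the adolescents who were unsuppressed at entry, so it complements the adjusted analysis of all participants and does not replace it.
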